3.9.3 Pain assessment

After a random treatment sequence was assigned to the study participants, the study participants will be guided on the operating manual for a 10-points, 100mm VAS pain score. The children will be presented with a ruler that contains 100-mm slots with “No Pain” written on the left side and “Worst Pain” on the opposite right side.

Before applying MN patch and EMLA Cream, the patients will be attached with the PainMonitor™ (Med-Storm Innovation AS, Oslo, Norway) device whereby the electrodes will be attached to the hypothenar eminence of the opposite hand not receiving the blood transfusion. The skin conductance peaks (in microSiemens (μ S) and the average rise time (in microSiemens per second (μ S/s)) will be recorded. Those parameters indicate the skin’s sympathetic nerve block induced by the applied EMLA cream.

After each procedure, the children then will be asked to move and place the slider in the slot that accurately describes his/her pain at the following time points: 1) 1 minute after application of MN/ sham patch and before EMLA Cream application (baseline VAS score); 2) 1 minute after IV cannulation. The investigator will record the location of the slot where the slider is placed in (millimetres (mm), clearly printed on the ruler’s backside) and this will be the participant’s VAS score. Throughout the process, there will be a trained nurse standing by at the day-care to assist the verification of the pain scale and to aid the participants who require additional assistance.

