For objective 2, we could not calculate the sample size since we don't have the estimate of the standard deviation of the differences (denoted by (s) henceforth) between the two methods for pain evaluation (the VAS score and the skin conductance algesimeter index obtained via PainMonitor™). Information on (s) is required since the sample size formula for evaluating limit of agreement require s parameters to be explicitly specified. However, we could roughly assess the precision of the limit of agreements (as per (s) magnitude) based on the sample size proposed for objective 1 and 2 using the formula recommended by the original authors.⁵² Based on Bland and Altman (1986), the 95% CI of limit of agreement is given by:

$$\pm 1.96 * \sqrt{3/n} * s^{52},$$

where s = standard deviation of the differences between VAS score and the skin conductance algesimeter index. If we assume a sample size of 24, then the precision of the limit of agreement is:

$$\pm 1.96 * \sqrt{3/26} * s = \pm 0.67 * s,$$

which we deem a satisfactory precision in our case.

However, due to absence of an estimate of (s) from prior studies, the actual precision could not be accurately estimated, thus highlighting the importance of (s) in the actual sample size calculation. Thus, it is hoped the estimate of (s) obtained from this study will be used as a guide for calculating a sample size for a future follow-up study that can answer this study objective more reliably. However,

Hence, the biggest overall sample size required for this study is 26 ($n_{\text{total}} = 26$).

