i) **VAS score (15- and 30-minutes post EMLA application during IV cannulation):** A continuous numerical variable that will be measured during each visit; 15 minutes after EMLA application and 30 minutes after EMLA application. Missing data will be recorded as 999 in the SPSS spreadsheet.

ii) **Pain score from PainMonitor™ device (15- and 30-minutes post EMLA application):** A continuous numerical variable that will be measured during each visit: 15 minutes after EMLA application and 30 minutes after EMLA application. Missing data will be recorded as 999 in the SPPS spreadsheet.

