For GLMM, the Restricted Maximum Likelihood (REML) estimator will be used to estimate the model parameters. The unadjusted and adjusted estimates of the parameters obtained using the GLMM will be examined, with and without the consideration of periodic effects. Random intercept model and robust variance estimators will be used for the calculation of standard errors. Likelihood ratio test will be utilized to compare the nested models and Akaike Information Criteria (AIC) and Bayesian Information Criteria will be used for comparing non-nested models. Multicollinearity between fixed effects (age, sex and treatment effects) will be evaluated using bivariate correlations. Besides, interaction effects (effect modification) between significant fixed predictors will also be assessed by evaluating the significance of interaction terms. Residual diagnostics will also be performed to ensure the validity of model assumptions and the presence of outliers and influential points will be investigated to ensure that they do not influence the model parameter estimates. The presence of any influential point will then be removed or corrected if these are due to measurement errors or wrong data entry or retained if the values are authentic. We will also carry out sensitivity analyses to investigate the effects of missing data under the Missing At Random (MAR) framework.

For the third and fourth objectives, the correlation between VAS pain score and PainMonitor™ device is tested using Pearson correlation coefficient if both VAS pain scores and PainMonitor™ device are normally distributed (Gaussian) and Spearman coefficient will be used if at least one pain scores (obtained by either measuring modality) are not normally distributed. Intraclass correlation coefficient (ICC) will be computed to assess the agreement between the VAS scores obtained using the two different modalities (VAS pain score vs PainMonitor™ device) and the results will be interpreted according to the Koo-Li criteria.⁵⁸ The Bland and Altman (B&A) plot will be obtained to further assess the agreement between the two scores. The limits of agreement obtained will be assessed to ensure there is an acceptable agreement between the pain measurement modalities.

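### Objective 3 plans an ICC and Bland-Altman limits between VAS in mm and a PainMonitor score with no visible unit or mapping to mm, so the agreement result depends partly on scale

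*Combined protocol and SAP*

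**What the plan says.** Sections 1.6, 2.2.3, 2.3.3 and 2.4.3 frame the third objective as agreement between VAS and the skin conductance algesimeter index. Section 3.14 plans three analyses for it:

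- a Pearson or Spearman correlation, chosen by normality;
- an ICC, introduced with "Intraclass correlation coefficient (ICC) will be computed to assess the agreement between the VAS scores obtained using the two different modalities", for which "the results will be interpreted according to the Koo-Li criteria". The form of the ICC is not stated;
- a Bland-Altman plot, about which the plan says "The limits of agreement obtained will be assessed to ensure there is an acceptable agreement between the pain measurement modalities". No acceptable value is given.

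On the VAS side, 3.9.3 fixes the unit: "The investigator will record the location of the slot where the slider is placed in (millimetres (mm", read off the back of the ruler. On the device side, the same section names two raw recordings: "The skin conductance peaks (in microSiemens" and an average rise time in microSiemens per second. Section 3.13 lists the analysed outcome as "Pain score from PainMonitor™ device (15- and 30-minutes post EMLA application" and describes it only as continuous and numerical. Nothing visible says which recording, or what function of the recordings, becomes the score.

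Section 3.12 defines s as the "standard deviation of the differences between VAS score and the skin conductance algesimeter index". It says that s is unknown, gives the 95% CI of a limit of agreement as ±0.67s, and regards that precision as satisfactory. That paragraph is labelled objective 2 although its content is objective 3, and 3.14 mentions a fourth objective although 2.2 lists three.

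**The concern.** An ICC and limits of agreement are meant for two measurements of one quantity on a common scale. Here one measurement is in mm and the other has no stated scale, and no rescaling step is planned. Computed as written, both statistics would partly describe the choice of units. The Koo-Li labels grade whatever ICC value comes out; they do not put the two scores on one scale.

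At stake is the reading of objective 3. Section 1.6 links it to pain monitoring in patients who cannot report pain, and 3.12 hopes that the estimate of s will size a follow-up study. A scale mismatch could get a useful monitor labelled as agreeing poorly, and an s in mixed units would be no basis for sizing another study.

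**Working it through.** **The plan's own figure.** Section 3.12 uses 1.96 × √(3/n) × s. With n = 26 this is 1.96 × √(3/26) = 0.666, so ±0.67s reproduces. The sentence introducing it says n = 24, which would give 1.96 × √(3/24) = 0.693, or ±0.69s. Either way the result is a multiple of s, and s is a raw subtraction of an undefined index from mm.

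**Inputs for the scale check.** The documents give no SD for either measure. I assume a VAS SD of SD1 = 20 mm and vary the index SD (SD2) from 0.15 to 18. The correlation r between the two is also assumed.

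**ICC.** For the single-measure consistency form, ICC = 2·r·SD1·SD2 / (SD1² + SD2²). For example, with r = 1 and SD2 = 5, 2 × 20 × 5 / (400 + 25) = 200/425 = 0.471.

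| Index SD | r = 1 | r = 0.7 | r = 0.5 |
|---|---|---|---|
| 0.15 | 0.015 | 0.010 | 0.007 |
| 1.5 | 0.149 | 0.104 | 0.075 |
| 5 | 0.471 | 0.329 | 0.235 |
| 10 | 0.800 | 0.560 | 0.400 |
| 18 | 0.994 | 0.696 | 0.497 |

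Within each column r is constant and only the scale changes. A simulation of 200,000 pairs at r = 0.5 and SD2 = 5 gave 0.237, against 0.235 from the formula.

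The absolute-agreement form adds (m1 − m2)² to the denominator. If VAS has mean 30 and SD 20, and the index is the same distribution divided by 10 (mean 3, SD 2), then at r = 1 it is 80 / (400 + 4 + 729) = 0.071, against 80/404 = 0.198 for consistency.

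**Limits of agreement.** s = √(SD1² + SD2² − 2·r·SD1·SD2).

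- SD2 = 0.15: s = 19.85 for a perfect monitor (r = 1) and 20.00 for a useless one (r = 0).
- SD2 = 10: s = 10.0 and 22.4.

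When the index has a small SD, s is essentially the VAS SD, and the limits barely separate the two monitors. The slope of difference on mean in the Bland-Altman plot, 2(SD1² − SD2²) / (SD1² + SD2² + 2·r·SD1·SD2), does not separate them either: at SD2 = 0.15 it is 1.97 for r = 1 and 2.00 for r = 0.

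**Repeated pairs.** The crossover gives each child several pairs. These figures assume four pairs per child, which the plan does not state, and 23 children (26 less dropout).

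- If pairs were pooled as independent, with a within-child correlation of 0.7 in both measures and no association, the variance factor is 1 + 3 × 0.7² = 2.47. A nominal 5% test would reject about 21% of the time; 20,000 simulations gave 21.7%.
- At r = 0.5, the within-child 95% CI by Fisher's z (68 df, SE 1/√67) is 0.30 to 0.66. The CI between child means (SE 1/√20) is 0.11 to 0.76.

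**The case against.** The strongest reply is that the same paragraph of 3.14 plans a correlation. Pearson's coefficient does not change under positive linear rescaling, nor Spearman's under any increasing transformation. A perfect and a useless monitor would show r near 1 and near 0, so a careful reader would not be misled by the ICC alone. This stands and limits the harm, but a correlation cannot answer a question posed as agreement.

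The objective is also secondary. Section 3.12 admits that s is unknown and defers a more reliable answer to a later study. That stands too.

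The SDs above are assumptions, and at an index SD of 18 the problem almost vanishes. The table shows sensitivity, not an expected error.

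A device range might appear in material not visible here: the figures in 1.5, Figure 5, the conceptual framework or the case report forms. That is possible. However, the definitions in 3.13 and the analysis text in 3.14 are readable and contain no scaling step, and a range alone would not map the index to mm.

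Three stronger readings are tempting but not supported:

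- From the phrase "10-points, 100mm VAS pain score" a reader might infer that VAS could be entered either in points or in mm. Section 3.9.3 makes the mm reading the VAS score, so this is only loose wording.
- A reader might infer that the pairs will be pooled as independent. Section 3.14 does not say how they are handled. Nor is four pairs per child stated: VAS is taken twice per visit and 3.13 includes a device baseline, so eight is possible.
- A reader might take comfort that the ICC cannot exceed r, so that a poor monitor could never be flattered. That holds for single-measure forms. An average-measures ICC with equal SDs at r = 0.5 is 2 × 0.5 / 1.5 = 0.67, and the plan does not state the form.

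**Conclusion.** The concern holds. As written, the ICC, the limits of agreement and s would be computed on scores with no visible common unit, and the result would depend on scale as well as on how well the index tracks pain. This goes beyond missing detail, because defining the device score would not by itself make raw-score agreement interpretable.

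Under the assumed VAS SD of 20 mm and the consistency form, the ICC of a perfectly correlated index can lie anywhere from 0.015 to 0.99 according to its SD. The true size cannot be given, because the documents provide no scale for the index. The point should be fixed before analysis. It does not touch the primary VAS comparison, and the planned correlation already contains part of the answer.

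**What to change.** 1. In 3.13, name the device variable that enters the analysis, its unit and range, and the time window paired with each VAS reading.
2. In 3.14, do not compute an ICC or limits of agreement on raw scores in different units. Restate objective 3 as association in 1.6, 2.2.3, 2.3.3, 2.4.3, 3.12 and 3.14.
3. Estimate the association with a method that accounts for repeated pairs within a child, for example child-mean and child-centred index values in a random-intercept model. Report within-child and between-child association with 95% CIs, plus a rank-based version. State how many pairs each child contributes.
4. Give limits of agreement only if the index is mapped to mm by an external or cross-validated calibration, against an acceptable limit in mm fixed beforehand. Fitting a calibration and testing agreement in the same 23 or so children would be optimistic.
5. In 3.12, remove the statement that the precision is satisfactory, since s in mixed units has no interpretation. Reconcile n = 24 with n = 26, and correct the objective numbering in 3.12 and 3.14.

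No additional data are needed. The cost is that the objective, research question and hypothesis change, and the claim softens from agreement to association.

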2.4 Research Hypotheses

- 2.4.1 There is at least a difference in terms of the VAS pain score means among the MN-with-1-FTU-EMLA (30-minute application time), MN-with-1FTU-EMLA (15-minute application time), MN-with-0.5 FTU-EMLA (30-minute application time), and 1-FTU-EMLA-only (30-minute application time) groups.
- 2.4.2 There is at least a difference in terms of the skin conductance algesimeter index means among the MN-with-1-FTU-EMLA (30-minute application time), MN-with-1FTU-EMLA (15-minute application time), MN-with-0.5-FTU-EMLA (30-minute application time), and 1-FTU-EMLA-only (30-minute application time) groups.
- 2.4.3 There is agreement between the VAS pain score and the skin conductance algesimeter index obtained via PainMonitorTM machine.

CHAPTER III

RESEARCH METHODOLOGY

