3.14 Planned Statistical Analysis

The data will be initially checked and cross-examined with the information in the data collection sheet for accuracy, consistency and the amount of missing data. Missing data will be treated as Missing At Random (MAR) and multiple imputation will be considered to impute the missing values in order to reduce the biasness of the parameter estimates. Any variable with serious missing data problem (more than 40%) will be dropped from further analysis.^{54,55} All patients will be analysed according to the original randomization group, based on the intention-to-treat (ITT) analysis.

All data will be descriptively summarized as mean and standard deviation (SD) for the normally-distributed numerical variables (or median and interquartile range (IQR) for the non-normally distributed numerical variables) and frequency and percentage for categorical variable. For numerical data, the normality assumptions will be evaluated subjectively using the histogram with overlying normal distribution curve, box and whisker plot and steam-and-leaf diagrams and objectively using the Kolmogorov-Smirnov and Shapiro-Wilks tests ($p>0.05$ indicates normal distribution assumption is met). Fisher's coefficient of skewness will be subsequently utilized to assess the severity of skewness in non-normally distributed numerical variables using the following formula:

Fisher's coefficient of skewness: Skewness / standard error of skewness

Any value outside ± 2 range will indicate extreme skewness.⁵⁶

For the first and second objectives, repeated measure ANOVA and generalized mixed effect model (GLMM) with an identity link function will be used to assess and estimate the differences in terms of VAS score means between the periods of interventions, considering intra-subject correlations. For repeated measure ANOVA, Mauchly's test of sphericity will be used to assess the sphericity assumption. If sphericity assumption is violated, the Greenhouse-Geisser correction will be used if $\varepsilon < 0.75$ or the Huynh-Feldt correction if $\varepsilon > 0.75$.⁵⁷ Within-group analysis will be used to assess the significance of mean VAS score differences between treatment pairs. To assess the presence of carryover effect, the within group-between treatment sequence interaction effect will be assessed for statistical significance.

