For each analysis, the significant threshold for p value is fixed at 0.05 and 95% confidence interval (CI) will be obtained for each parameter estimates. Data analysis will be performed using Statistical Package for Social Science (SPSS™) (IBM Corp. Released 2020. IBM Statistics for Windows, Version 27.0, Armonk, NY: IB Corp) and STATA™ version 15 (StatCorp. 2017. Stata Statistical Software: Release 15. College Station, Texas: StataCorp LP).

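### Pairwise VAS tests at 0.05 have no multiplicity rule, and an overall-test gate alone would not protect the dose and time conclusions; separately, REML likelihood ratios are used to compare fixed effects

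*Combined protocol and SAP*

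**What the plan says.** The regimens are A (microneedle, 1 FTU, 30 minutes), B (microneedle, 0.5 FTU, 30 minutes), C (microneedle, 1 FTU, 15 minutes) and D (1 FTU alone, 30 minutes, control). VAS is the primary endpoint (section 3.9.2).

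- The VAS hypothesis in section 2.4 is an overall one: "There is at least a difference in terms of the VAS pain score means among the" four regimens. Section 3.12 sizes the trial for that overall test (alpha 0.05, power 0.80, 23 completers, 26 enrolled).
- Section 3.14 names both repeated-measures ANOVA and a mixed model for VAS, and adds: "Within-group analysis will be used to assess the significance of mean VAS score differences between treatment pairs". The threshold is general: "For each analysis, the significant threshold for p value is fixed at 0.05".
- No section adjusts the pairwise tests, makes them conditional on the overall test, or says which pairs are confirmatory.
- For the mixed model, "the Restricted Maximum Likelihood (REML) estimator will be used to estimate the model parameters". Unadjusted and adjusted estimates are examined "with and without the consideration of periodic effects", and "Likelihood ratio test will be utilized to compare the nested models". The only random effect planned is an intercept, and no ML refit is mentioned. Later, "interaction effects (effect modification) between significant fixed predictors will also be assessed".

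**The concern.** The overall test can show that some regimen differs, but not that B or C does. Section 1.6 gives a reduced dose and a faster action as the reason for the study, so the statements the trial is meant to support rest on the pairs. The error rate for those statements is left unset.

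The likelihood ratio is a separate matter. A restricted likelihood is the likelihood of data contrasts from which the fixed effects have been removed. Two models with different fixed effects use different contrasts, so the ratio does not compare two fits to the same data. Verdicts on period and covariate terms would then be unreliable.

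**Working it through.** **The plan's own figure.** The 23 is for the overall F test with 4 measurements and epsilon 0.75. The degrees of freedom are 3 × 0.75 = 2.25 and 22 × 2.25 = 49.5. With 0.8 entered as f and noncentrality f² × N × epsilon = 0.64 × 23 × 0.75 = 11.04, power is 0.815. The same 11.04 follows from f = 0.4 with r unused: 4 × 23 × 0.16 × 0.75. Drop-out: 23 / 0.9 = 25.6, so 26. The 0.80 is therefore power for the overall test, not for any pair.

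**Inputs for the error rates.** 23 and 26 completers and r = 0.7 (section 3.12); threshold 0.05 (section 3.14). Assumed: two-sided tests (sidedness is not stated), normal data, equal correlations. Under equal correlations, the differences A-D and B-D have covariance 1 - r and variance 2(1 - r) each, so they correlate 0.5 whatever r is. The ungated null rates therefore do not depend on r.

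**Simple bounds.** Three independent tests give 1 - 0.95³ = 14.3%. Two give 1 - 0.95² = 9.75%. The shared control lowers both slightly.

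**Simulation (at least 40,000 trials per setting, 23 and 26 completers).**

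| True state | Rule | False microneedle-vs-control difference |
|---|---|---|
| Nothing differs | no gate | 12.3-13.0% (benefit direction 6.1-6.4%) |
| Nothing differs | overall F first | 3.9-4.1% |
| Only A differs, by 0.5-0.8 SD | overall F first; B or C vs D | 8.8-9.2% (benefit direction 4.5-4.6%) |
| Only A differs, by 0.5-0.8 SD | Holm over A, B, C vs D | 4.1-4.9% |

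In the third row, A's real effect opens the gate and two null pairs are then tested at 0.05 each, close to the 9.75% bound. In the fourth row, once A is rejected, Holm's next threshold is 0.05/2 = 0.025, so the bound for the two null pairs is 2 × 0.025 = 5%.

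**Power for one contrast at N = 23, two-sided paired t, at 0.05 and at Holm's strictest step (0.05/3 = 0.0167).**

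| Reading of section 3.12 | Standardised paired difference | 0.05 | 0.0167 |
|---|---|---|---|
| d = 0.8 and r = 0.7 both hold | 0.8/√0.6 = 1.033 | 99.7% | 98.7% |
| 0.8 is the paired difference itself | 0.8 | 95.6% | 88.3% |
| f = 0.4, r unused, one arm differs | 0.653 | 85% | 70% |
| d = 0.8, r unused | 0.8/√2 = 0.566 | 74% | 56% |

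**REML likelihood ratio for period (3 df, cut-off 7.81), no true period effect.** With VAS in mm, as section 3.9.3 records it, and an assumed SD of 15, 20 or 30 mm, all of 2,000 simulated null trials per setting rejected. ML fits rejected in roughly 6-9%. At SD 20 mm the REML statistic averaged 14.9, with minimum 10.6.

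Dividing VAS by 10 adds (n - p) × ln 10 to a restricted log-likelihood with n observations and p fixed effects. The statistic for 3 extra terms therefore moves by -2 × 3 × ln 10 = -13.8. In cm the mean becomes 14.9 - 13.8 = 1.1 and the minimum 10.6 - 13.8 = -3.2, a negative value that a proper nested likelihood ratio cannot take. Simulated rejection in cm is about 1-2%. An age term behaves the same way (600 null trials per unit, 26 children): 17.5% rejection with age in years and 1.7% in months, against 6-7% with ML.

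**Effect on treatment estimates.** Keeping period terms raises the treatment standard error by 0.4% on average (maximum 4%) and moves the estimate by 0.07 standard errors.

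**The case against.** The usual reading of a repeated-measures ANOVA followed by pairs is that the pairs are looked at only after a significant F. On that reading the null rate is about 4%, and the hypothesis and sample size are both overall. This stands as a limit on the 13%, which is not the rate of the plan as written, because the plan leaves the gate open. It does not remove the point: the gate fails when one regimen works and the question is whether the lower dose or shorter time does too.

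Roughly half of the false findings would say that the microneedle is worse. That is right, and the benefit-direction rates are given for that reason.

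This is a single-centre phase II trial, its general objective (section 2.1) is with versus without microneedle, and section 3.13 codes control as the base category. These make A, B and C versus D the natural family. They do not declare it confirmatory or set its error rate.

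On the likelihood ratio, section 3.14 does not say outright which nested models are compared. It reports estimates with and without period, so the test need not choose a model, and it does not say that interactions are judged by likelihood ratio. This stands, and the practical consequence is modest. But the only model differences described are in fixed effects, and REML is the only estimator named.

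**Conclusion.** The gap in the pairs is real. Without a gate the null rate is about 13%, and with one about 4%. With a gate and only A working, false B or C findings occur in about 9% of trials (about 4.6% towards benefit), against 4-5% with Holm. These figures rest on 23 to 26 completers, r = 0.7, equal correlations and two-sided tests. The likelihood ratio wording is wrong for fixed effects; verdicts on period and covariate terms are affected, while treatment contrasts barely change.

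Three stronger readings are not supported:

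- A reader might infer that the trial has a 13% false-positive rate. The overall VAS hypothesis is tested at close to 5% (5.3% simulated), and a gate is not excluded.
- A reader might infer that REML would always declare a period effect. That holds in mm and reverses in cm; the sound statement is that the test is invalid and unit-dependent.
- A reader might add that robust standard errors are too small with so few children. The plan names no reference distribution, so an error rate would rest on an assumed one, and no point is made of it.

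**What to change.** 1. In section 3.14, name A, B and C each versus D as the confirmatory VAS contrasts with Holm adjustment, state whether the repeated-measures ANOVA or the mixed model supplies the p-values, and report the other pairs descriptively. The cost is power per contrast at N = 23: 1 percentage point if d = 0.8 and r = 0.7 both hold, and up to 18 points (74% to 56%) on the least favourable reading of section 3.12. No extra children are asked for. Section 3.12 should describe its 0.80 as power for the overall test.
2. Alternatively, declare the overall test the only confirmatory VAS test and report all pairs as estimates with 95% confidence intervals, without significance claims. This needs no adjustment, but it gives up confirmatory claims on dose and time.
3. State that any likelihood ratio comparison of models with different fixed effects uses ML fits, and keep REML for final estimates. This is a change of wording and close to free.
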